For the patients in the Pecs group, a linear ultrasound probe was placed on the lateral third of the clavicle with bilateral abduction in the supine position. After identifying the axillary vein and artery, the ultrasound probe was positioned inferio-laterally, between the 3rd and 4th ribs, and then the pectoralis major and minor, and serratus anterior muscles were confirmed. The needle was advanced in a medio-lateral direction in-plane view of the ultrasound. For the Pecs II block, a total 30 mL of 0.5% ropivacaine was injected. First, the needle tip was advanced into the fascia between the pectoralis major and minor muscles and 10 mL of 0.5% ropivacaine was injected. Thereafter, the needle tip was advanced into the tissue plane between the pectoralis minor and serratus anterior muscles, and 20 mL of 0.5% ropivacaine was injected in a similar manner.

Fifteen minutes after the Pecs II block, a skin incision was made for the scheduled surgery. During

the surgery, the remifentanil dose was adjusted to a target SPI of 20–50 and the propofol dose was adjusted to a target BIS of 40–60, using a TCI pump. When the SPI was >50 or <20, the remifentanile effect-site concentration was adjusted to a step of 0.5 ng/kg with intervals of 1 min or more. When the BIS value was >60 or <40, the propofol effect-site concentration was adjusted to a step of 0.5 g/kg with intervals of 1 min or more. When the systolic blood pressure dropped below 90 mm Hg or below 80% of the baseline value, ephedrine 5 mg was administered intravenously at 2-min intervals. If the heart rate (HR) dropped below 50 beats/min, atropine 0.5 mg was administered intravenously.

Patient-controlled analgesia (PCA) (Accufuser plus®, Wooyoung medical, Seoul, Korea) was provided for 48 h with ketorolac 120 mg and sufentanil 50 g in normal saline 100 mL, (basal infusion rate 2 mL/h, 0.5 mL intermittent bolus with a 15 min lock-out interval). For preventing PONV, ramosetron 0.3 mg was administered intravenously before the end of the surgery.

In the postanesthetic care unit (PACU), the postoperative pain was evaluated using an 11-point numerical rating scale (NRS) (0–10) and was accessed immediately after arrival at the PACU, 1 h postoperatively, 16–24 h postoperatively, and 24–48 h postoperatively. Fentanyl 50 g bolus was administered as a rescue analgesic agent when the NRS was greater than 5 points.

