The primary outcome was the intraoperative remifentanil consumption, and the secondary outcomes were the postoperative pain score and rescue analgesic requirement. The sample size was calculated based on the previous study of breast cancer surgery under TIVA. The intraoperative remifentanil consumption was 10.9 2.9 g/kg/h and 7.3 3.3 g/kg/h in the control and Pecs groups, respectively. With type 1 error of 0.05 and a power of 0.9, the study required 14 patients in each group. Considering the possible drop-out, 20 patients were included in each group. Patients were randomly assigned to the Pecs group (n = 20) or the control group (n = 20), based on a randomized list generated with Excel 2013 (Microsoft office, Redmond, WA, USA), without stratification.

Data were analyzed using SPSS 19.0 (SPSS, Chicago, IL, USA). Values were presented as number of patients, medians (interquartile ranges; IQR) or mean standard deviation (SD). The Kolmogorov-Smirnov test was performed for the normality test of continuous variables. The normally distributed data were presented as mean SD and the skewed data were presented as median (IQR). An independent t-test was used for normally distributed variables (intraoperative dosages of remifentanil and propofol), and the Mann–Whitney U Test was used for variables with a non-normal distribution (postoperative pain scores). The chi-squared test or Fisher's exact test was

used to analyze the categorical data (the use of atropine, ephedrine and rescue analgesics), where appropriate. Repeated, measured ANOVA was used for accessing the intergroup differences of MBP, HR, SPI, and BIS over time. Statistical significance was accepted for p value < 0.05.

Primary completion date : December 30, 2018

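### MBP and HR are compared by repeated-measures ANOVA without a baseline covariate, which loses precision (but causes no bias) on two measures outside the listed outcomes

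*Combined protocol and SAP*

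**What the plan says.** The combined protocol and SAP has no numbered sections, so places are given by paragraph.

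- **Statistical paragraph.** The whole plan for these measures is "Repeated, measured ANOVA was used for accessing the intergroup differences of MBP, HR, SPI, and BIS over time". It does not list the measurement times, say whether a baseline reading is one of them, say whether the group effect or the group-by-time effect is tested, or mention a covariate.
- **Intraoperative management paragraph.** Ephedrine is triggered by "When the systolic blood pressure dropped below 90 mm Hg or below 80% of the baseline value". This needs a baseline systolic pressure for each patient, but the time of that reading is not given. Heart rate is handled by an absolute limit: "If the heart rate (HR) dropped below 50 beats/min, atropine 0.5 mg was administered intravenously". No baseline HR is involved.
- **Monitoring paragraph.** ECG and non-invasive blood pressure are applied in the operating room. The text describes this ahead of the induction drugs, but does not say that MBP or HR was recorded at that point.
- **Outcomes.** "The primary outcome was the intraoperative remifentanil consumption, and the secondary outcomes were the postoperative pain score and rescue analgesic requirement". MBP and HR are in neither group.
- **Design.** 20 patients per arm, randomised from a list without stratification.

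**The concern.** MBP and HR differ between patients in a fairly stable way. A reading taken before the block carries much of that variation and cannot itself be affected by the block. A model that ignores it leaves the variation in the error term. A model that enters it as one more response averages the treatment effect with a time point where the effect must be zero.

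At stake is how well the trial can show whether the block leaves patients haemodynamically different during surgery. MBP and HR are its only continuous haemodynamic measures; ephedrine and atropine use are analysed as categories. With 20 per arm there is little precision to spare.

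SPI and BIS share the same sentence, but they are steered to target ranges by dose adjustment, so the point is made for MBP and HR only.

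**Working it through.** **The plan's own figure.** None is stated for MBP or HR. The only sample size is for remifentanil consumption: difference 10.9 − 7.3 = 3.6, pooled SD √((2.9² + 3.3²)/2) = 3.106. The two-sided normal formula gives 15.65, so 16 per group with the pooled SD, and 14 with SD 2.9, against the stated 14. That calculation is separate from this point and is unaffected by it.

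**Inputs for MBP, all assumed except n.** n = 20 per arm (documents, with no drop-out); SD 12 mm Hg; k = 5 intraoperative readings; correlation 0.7 among them; constant true shift 8 mm Hg; correlation r between baseline and each later reading of 0.3, 0.5 or 0.7.

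**Variance of each patient's summary, in units of SD²**
- Baseline left out (mean of 5): (1 + 4 × 0.7)/5 = 0.76.
- Baseline as a level (mean of 6): (1 + 25 × 0.76 + 10r)/36 = (20 + 10r)/36. The effect becomes 8 × 5/6 = 6.67 mm Hg.
- Baseline as covariate (ANCOVA on the mean of 5): 0.76 − r².

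**Standard error and power for the group effect.** SE = 12 × √(2v/20), where v is the variance above. Power is from the t distribution, two-sided 5%. At r = 0.5:

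| Analysis | v | SE (mm Hg) | Effect/SE |
|---|---|---|---|
| Baseline as a level | 0.694 | 3.16 | 6.67/3.16 = 2.11 |
| Baseline left out | 0.76 | 3.31 | 8/3.31 = 2.42 |
| ANCOVA | 0.51 | 2.71 | 8/2.71 = 2.95 |

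| Power | r = 0.3 | r = 0.5 | r = 0.7 |
|---|---|---|---|
| Baseline as a level, main effect | 57% | 54% | 51% |
| Baseline left out, main effect | 65% | 65% | 65% |
| ANCOVA | 71% | 82% | 98% |

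Simulation (4,000 trials per correlation) agrees within about 2 points, with ANCOVA at 70%, 81–82% and 97%. Type I error is about 5% for all three.

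**If group-by-time is the test.** Same assumptions, Greenhouse–Geisser correction, 4,000 simulated trials per correlation:
- Baseline as a level: about 44%, 55–56% and 74–76% at r = 0.3, 0.5 and 0.7, which is still more than 20 points below ANCOVA.
- Baseline left out: about 5%. A constant shift produces no interaction, so only the false-positive rate remains.

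**Sensitivity to the assumptions.** Let all readings, baseline included, share one correlation ρ.
- Dilution factor k/(k + 1): 0.75, 0.83 and 0.89 for k = 3, 5 and 8.
- ANCOVA variance relative to leaving baseline out, with v = (1 + (k − 1)ρ)/k, is (v − ρ²)/v. For k = 3, ρ = 0.3: (0.533 − 0.09)/0.533 = 0.83. For k = 5, ρ = 0.5: (0.60 − 0.25)/0.60 = 0.58. For k = 8, ρ = 0.7: (0.7375 − 0.49)/0.7375 = 0.34.
- At k = 5, ρ = 0.5 and a shift of 0.8 SD, power is 77% (baseline as a level), 89% (left out) and 99% (ANCOVA). The ordering holds, but the absolute levels depend on the assumed shift.

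These ratios have no units, so they apply to HR as well if its correlations are similar. No separate HR figure can be derived.

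**The case against.** The strongest case against has five parts.

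- **The MBP and HR baseline is not documented.** A reader might infer that the protocol already uses a pre-anaesthesia baseline for both. It does not: the only baseline is systolic, with undefined timing, and HR has a fixed limit. This stands. A pre-induction MBP and HR reading is a reasonable inference from the monitoring, not a stated fact, so the remedy must be conditional on its having been recorded.
- **Dilution depends on an unspecified test.** It applies only to the main effect with baseline as a level. The plan's reference to differences over time may mean the interaction, where the effect is not averaged with a zero and a constant baseline difference cancels. This stands as a limit on the dilution claim. It does not rescue the plan, because the interaction is also less efficient than ANCOVA for a sustained shift.
- **Bias.** A reader might infer that chance baseline imbalance would be mistaken for a block effect. Under the assumed SD the baseline difference has SE 12 × √(2/20) = 3.8 mm Hg, so a gap of several mm Hg in one trial would be ordinary. But randomisation keeps the unadjusted comparison of later readings unbiased on average, and the 5% error rate already allows for such gaps.
- **Missed effects.** A reader might also infer that a real difference would probably be missed. The illustrated main-effect powers of 51% to 65% do not say that, and the documents supply no shift against which to judge it.
- **Low stakes and late timing.** MBP and HR are not listed outcomes, and the document is dated June 16, 2019, after primary completion on December 30, 2018. Both facts stand; they limit the importance of the point and determine how the fix must be labelled.

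**Conclusion.** The point holds as a modest loss of precision. The plan names no baseline adjustment for MBP or HR, and under each of the four readings of its sentence examined here, adjustment has more power for a sustained shift.

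With 20 per arm, SD 12 mm Hg, five readings correlated at 0.7, a shift of 8 mm Hg and baseline correlation 0.5, main-effect power is about 54% to 65%, against about 82% with ANCOVA. At baseline correlation 0.3 the gain over leaving baseline out is only about 5 points. Over k = 3 to 8 and a common correlation of 0.3 to 0.7, ANCOVA variance is 0.83 to 0.34 of the unadjusted variance. None of these SDs, correlations, reading counts or shifts is in the documents, so the direction is firm and the size is illustrative.

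The documents do not support a claim of bias or inflated type I error, nor any effect on the remifentanil comparison, its sample size or the two secondary outcomes.

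**What to change.** Add a supplementary analysis of MBP and HR, labelled as such because the document post-dates primary completion:

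1. List the measurement times used.
2. Use only post-block readings as responses, with readings at matching times in the control group. Do not enter baseline as a time level.
3. Include the pre-block or pre-induction value of the same measure as a covariate where it was recorded, taken at a comparable moment in both arms.
4. Report the baseline-adjusted group difference with its 95% CI.
5. For the repeated-measures ANOVA already described, state whether baseline was a level and whether the group or group-by-time effect was tested.

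The cost is one degree of freedom for each measure (38 to 37 with 40 patients) and a few lines of text, with no new patients or visits. If no baseline MBP or HR was recorded, steps 1, 2 and 5 still apply, and the report should say that the comparison is unadjusted.
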